## 6 STUDY PROCEDURES

6.1 Participants will be assigned to one of three intervention groups (Table 2).

Groups	Subcutaneous injectate	Intravenous injectate*
SC (n=20)	50 mg/ml ketamine	0.9% Sodium Chloride
IVI (n=20)	0.9% Sodium Chloride	50 mg/ml ketamine
P (n=20)	0.9% Sodium Chloride	0.9% Sodium Chloride

**Table 2:** Intervention groups. \*the i.v. injectate will be diluted up to a 40 ml infusion.

6.2 Participants will have baseline data (Table 3) recorded on the relevant case report form on the day of delivery. This data will include demographics to assess the performance of randomization procedures as well as characteristics that have been demonstrated to confer an increased risk of PPD. The patient will be prepared for cesarean as per institutional protocols.

Measure	Units/values
Age	Years
Height	Metres
Weight (day of surgery)	Kilograms
Gestational age	Weeks
Ethnicity	White, Black/African American, Asian, Native American/Alaskan natives, Native Hawaiian, Pacific Islander, Hispanic/Latino
Insurance status	Insured/uninsured
Psychiatric history	PPD, major depressive disorder (MDD), anxiety, premenstrual syndrome (PMS), premenstrual dysphoric disorder (PMDD), mood disorder, personality disorder, psychotic disorder
Current anxiety and depressive symptoms	EPDS and GAD-7
Psychosocial stress	ANRQ

**Table 3:** Baseline data

Once an adequate sensory block is achieved, surgery will commence. Upon delivery of the baby, 0.01 ml/kg of the “*subcutaneous injectate*” will be injected subcutaneously and the “*intravenous injectate*” will be made up to a 40ml infusion (Table 4) and commenced at 60 ml/hr. Both injectates will be administered/initiated approximately 0 - 5 minutes after delivery by the anesthetic provider via one of the cannulae that they will be using for standard patient care. The intravenous study infusion will be prepared by a member of the investigative team, who will not be involved in data collection.

---

Add 0.01 ml/kg of the “*IVI study solution*” to a 60ml syringe and use 0.9% sodium chloride to dilute the solution to 40ml.

---

**Table 4:** Instructions for preparing the “*IVI study infusion*”

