## SYNOPSIS

Study Title	Postpartum depression after Cesarean delivery: Ketamine as a preventative intervention. A feasibility pilot-study (PoCKet Pilot).												
Primary Objective	To assess the feasibility of the study by establishing: a) the incidence of PPD in our cohort; b) the acceptability to eligible patients; c) the ability of the investigative team to collect the data and; d) the tolerability of the interventions.												
Hypothesis	We hypothesize that ketamine reduces the incidence of postpartum depression (PPD) when administered at cesarean delivery and that the subcutaneous route is well tolerated and has a favorable pharmacokinetic profile.												
Study Period	Planned enrolment duration: 52 weeks Planned study duration: 58 weeks												
Number of Participants	60 patients (20 in each of the subcutaneous [SC], intravenous [IVI] and control [P] groups)												
Study Intervention	Patients in each group will receive both subcutaneous (s/c) and intravenous (i.v.) administration of their corresponding injectate shortly after delivery of their baby. The injectate will consist of either 0.9% Sodium Chloride (N/S) or 50 mg/ml ketamine (Ket) depending on their group allocation. The s/c injectate will be administered undiluted whereas the i.v. injectate will be diluted to make up a 40 ml infusion. 
  
 Groups	s/c injectate	i.v. injectate	
   
 SC:	Ket	N/S	
 
 IVI:	N/S	Ket	
 
 P:	N/S	N/S	
  
	Groups	s/c injectate	i.v. injectate	SC:	Ket	N/S	IVI:	N/S	Ket	P:	N/S	N/S
Groups	s/c injectate	i.v. injectate											
SC:	Ket	N/S											
IVI:	N/S	Ket											
P:	N/S	N/S											
Study Design	A randomised, double-blind, placebo-controlled feasibility pilot study												

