### 1.3 Ketamine and PPD

This promising anti-depressant effect has prompted investigation of ketamine as a preventative measure in patients undergoing CD. There have been 2 studies to date, one which failed to demonstrate any benefit from a bolus dose of 0.25 mg/kg and one which documented a large reduction (1 and 22% in the treatment and control, respectively) in the (6 week) period prevalence of postpartum depression after a 4 mg/kg dose of ketamine over 50 hours (~0.08 mg/kg/hr).

The prolonged IV infusion, in the Jianxin (2015) study, was achieved by adding the ketamine to a sufentanil patient-controlled analgesic (PCA) pump with a background infusion. This PCA pump is a standard part of their post-cesarean analgesic regimen. In our institution, it is standard practice to discontinue IV infusions and to remove IV cannulae as early as it is safe to do so. This practice is essential to the attempts to enhance postoperative recovery and aid mother's bonding with their babies and facilitate their early-

life care. This reflects patients' expectations and preferences and is in line with other maternity units across North America and Europe.

The natural course of PPD varies and, although it may resolve spontaneously within weeks, approximately 20% of women with PPD still have depression at 12 months and beyond. As many as 13% will still have depressive symptoms at 2 years and 40% will have a relapse. Considering the maternal suffering, disruption to the family, potential impairment of the social, emotional, and cognitive development of the child, and the rare cases of infanticide and suicide caused by PPD, the impact on families and society as a whole is difficult to overemphasize. An intervention that promises such a large reduction in this devastating disease warrants extensive research. In an attempt to achieve the benefit demonstrated by Jianxin et al. whilst employing methods more acceptable to our patients we have designed a pilot study to assess the feasibility of our study design and collect preliminary tolerability and efficacy data on ketamine administered by two alternative routes: 40-minute IV infusion (i.v.) and subcutaneous (s.c.) injection.

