## 2 OBJECTIVES

- 2.1 To determine the feasibility of performing this study at our institution
- 2.2 To determine the pharmacokinetic profiles of ketamine when administered as a subcutaneous injection and an intravenous infusion at cesarean delivery
- 2.3 To obtain preliminary data to inform the design of a randomized controlled trial to assess the efficacy of ketamine as a preventive intervention at cesarean delivery against PPD

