### 9.2 Pharmacokinetic analysis

NONMEM® 7.4 (ICON Development Solutions) software will be utilised to assess pharmacokinetic profile of ketamine by each route.

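### Does section 6.2 direct the subcutaneous injectate through a cannula, against the rest of the protocol?

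*Combined protocol and SAP*

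**What the plan says.** The synopsis (Study Intervention) sets up a double-dummy scheme: "Patients in each group will receive both subcutaneous (s/c) and intravenous (i.v.) administration of their corresponding injectate shortly after delivery of their baby". It separates the two products by preparation: "The s/c injectate will be administered undiluted whereas the i.v. injectate will be diluted to make up a 40 ml infusion". Section 1.3 names the two alternatives under study as "40-minute IV infusion (i.v.) and subcutaneous (s.c.) injection", and objective 2.2 is "To determine the pharmacokinetic profiles of ketamine when administered as a subcutaneous injection and an intravenous infusion at cesarean delivery". Table 2 has one column for each injectate, headed by its route.

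The working instruction is in section 6.2. It states that 0.01 ml/kg of the subcutaneous product "will be injected subcutaneously" and that the intravenous product is made up to 40 ml and run at 60 ml/hr. The sentence after that reads "Both injectates will be administered/initiated approximately 0 - 5 minutes after delivery by the anesthetic provider via one of the cannulae", and goes on to describe these as cannulae in use for the patient's ordinary care.

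The only other mention of cannulae is in the background, section 1.3, where the institution reports that "it is standard practice to discontinue IV infusions and to remove IV cannulae as early as it is safe to do so".

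**The concern.** The grammatical subject of the cannula sentence is both injectates, with no exception for the subcutaneous one. No subcutaneous cannula is described anywhere, and the other mention of cannulae is of intravenous ones. Read strictly, two adjacent sentences therefore give the same product two different routes. This is also the only text that states the subcutaneous volume and who gives it, so it is where a provider would look.

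Route matters in this trial. The active arms match on amount, so an SC participant dosed through a cannula would not represent the SC arm. That would bear on objective 2.2, on the section 9.2 analysis meant to "assess pharmacokinetic profile of ketamine by each route", and on the arm-level tolerability milestone FM4 (section 8.1.4). With 20 participants per arm, one misallocated route is not negligible.

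**Working it through.** No figure in the plan is in dispute. The check is a comparison of texts, with a little arithmetic to show what depends on route.

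**What separates the active arms.**
- SC arm: 0.01 ml/kg (section 6.2) x 50 mg/ml (Table 2) = 0.5 mg/kg, undiluted (synopsis).
- IVI arm: 0.01 ml/kg (Table 4) x 50 mg/ml (Table 2) = 0.5 mg/kg, diluted to 40 ml. At 60 ml/hr the infusion lasts 40 / 60 hr = 40 minutes, which reproduces the duration in section 1.3.
- The amounts are equal, so the arms differ only in route and manner of giving.

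**Who could be affected.** Table 2 puts ketamine in the subcutaneous syringe only in the SC group: 20 of 60. In the IVI and P groups that syringe holds saline, so a misreading there would not change ketamine exposure.

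**How sensitive FM4 is.** An arm fails when more than 10% of its participants have a severe side effect. Since 0.10 x 20 = 2, failure needs at least 3 participants. One participant is a third of that count. This describes the rule's sensitivity and does not predict any misreading.

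**Route of the subcutaneous injectate, place by place.**

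| Place | What it gives |
|---|---|
| Section 6.2, preceding sentence | Subcutaneous injection |
| Table 2 | Separate subcutaneous and intravenous columns |
| Synopsis, Study Intervention | Two routes for every participant |
| Section 1.3 | Subcutaneous injection as an alternative to infusion |
| Objective 2.2 | A kinetic profile for each of the two routes |
| Section 6.2, cannula sentence | Both injectates through a care cannula, type not stated |

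Five places agree and one phrase differs. The product's own name also carries its route.

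**Reading the odd sentence.** It mainly fixes timing and operator. Its two verbs, administered and initiated, match two products: an injection is administered and an infusion is initiated. The cannula phrase then belongs to the infusion. Section 6.2 does not call the cannulae intravenous. That is inferred from their being in use for ordinary care and from section 1.3, so the conflict itself rests on one inference.

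**Timing.** Section 6.2 places dosing upon delivery and within about 0 to 5 minutes of it, and the synopsis places it shortly after delivery. These statements are compatible, so there is no timing conflict.

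**The case for a change.** The strongest case for acting is that the sentence's grammar does not make the split between injection and infusion; the reader has to supply it from elsewhere. The other sections show the intent without amending the sentence. The person addressed is busy with an operation and, in a double-blind trial, should not be able to tell from the syringe's contents which product matters. Correcting one sentence costs almost nothing.

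Much of that stands. The wording is faulty, and the two sentences should agree on route. What does not stand is the step from faulty wording to damaged results. A provider would have to take a product labelled by its subcutaneous route, just described as a subcutaneous injection, and give it through a cannula. Nothing in the documents suggests this would happen.

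It can also be said that sections 9.1 and 9.2 contain no rule for analysing administration deviations. That is true, but it would be equally true if this sentence were perfect, so it adds no weight to this point.

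**Conclusion.** This is a clerical slip, and no change to the plan follows. In section 6.2 the cannula phrase grammatically covers both injectates, while the preceding sentence, Table 2, the synopsis, section 1.3 and objective 2.2 keep the routes apart. The sponsor should reconcile the two sentences on route when the text is next edited. That edit alters no allocation, sample size, endpoint, analysis or conclusion.

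The effect on results cannot be quantified, because the documents give no misreading rate. Its reach is bounded by the 20 SC participants. The conclusion rests on two assumptions: that the cannulae are intravenous, without which there may be no conflict at all, and that providers follow the explicit route statement and the product name over a loosely attached phrase. No position is taken on dose, route or any other clinical choice.

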### Measurements:

1. Baseline data
2. EPDS and GAD-7 scores at baseline and approximately 1, 2, 21 and 42 days postpartum

3. ANRQ at baseline
4. Time of delivery of baby
5. Total intraoperative dose of any analgesic/sedative medication
6. Incidence of hypo- or hypertension (systolic BP < 80 or > 170 mmHg, respectively) and brady- or tachycardia (pulse < 40 or > 120 bpm, respectively)
7. Maximum intraoperative pain (numerical rating scale [NRS], 0-10)
8. Incidence of the signs/symptoms in Table 5 will be assessed intraoperatively and approximately 2 and 6 hours after delivery. The presence of each adverse effect will be assessed using a 4-point scale (absent, mild, moderate, severe).

Nausea	Shivering	Blurred vision
Vomiting	Anxiety	Diplopia
Pruritus	Euphoria	Nystagmus
Dizziness	Hallucinations	
Sedation	Amnesia	

**Table 5:** Adverse effects

9. Surgical site pain (NRS) at 2, 6, 24 and 48 hours, as well as 21 and 42 days, postpartum.
10. Opiate consumption in the first 48 hours (measured in morphine equivalents) will be calculated.
11. Plasma concentrations of ketamine at baseline and approximately 20, 40 and 100 minutes postpartum.

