Eligibility Criteria	
Inclusion criteria
 
 
1. Term pregnancy
 
2. Age 18-45 years of age
 
3. Scheduled cesarean delivery under neuraxial anesthesia
 
 
Exclusion criteria
 
 
1. ASA classification IV or V
 
2. History of psychotic episodes
 
3. History of allergy to ketamine
 
4. Inability to communicate in English or any other barrier to providing informed consent
 
												
Measurements	
 
Psychosocial stress (Antenatal Risk Questionnaire [ANRQ])
 
Weight (kg) and height (m)
 
Time of delivery of baby
 
Total intraoperative dose of analgesic/sedative medication
 
Baseline and intraoperative vital signs
 
Maximum intraoperative pain (NRS)
 
48-hour total opiate consumption (morphine equivalents)
 
Apgar scores at 1 and 5 minutes postpartum
 
Admission to NICU
 
												

	
 
j) Pain originating from surgical site (NRS 0-10): 2, 6, 24 and 48 hours and 21 and 42 days postpartum.
 
k) Edinburgh Postpartum Depression Scale (EPDS) and Generalized Anxiety Disorder 7-item (GAD-7) Scale: Day of surgery and postpartum days 1, 2, 21 and 42
 
l) Plasma concentrations of ketamine at baseline, 20, 40 and 100 minutes after administration
 
m) Breastfeeding success (Y/N): postpartum days 1 and 2
 
n) Adverse effects, intraoperatively and at 2 and 6 hours postpartum (absent, mild, moderate or severe)
 

Statistical Methodology	
Descriptive statistics will be employed to present the demographic data. Continuous variables will be summarized using means (SD) or medians (IQR), as appropriate. After construction of the concentration-time curves for each patient, the peak plasma concentration and area under the concentration-time curve will be summarized overall and associations with both antidepressant effect and incidence of adverse symptoms will be explored.
 
NONMEM® 7.4 (ICON Development Solutions) software will be utilised to assess pharmacokinetic profile of ketamine by each route.

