## 4 REGISTRATION PROCEDURES

- 4.1 Confirmation of patient eligibility
  - 4.1.1 We will screen all patients scheduled for cesarean delivery and confirm their eligibility by assessing their: i) age; ii) gestational age; iii) medical history and; iv) allergy history.
- 4.2 Assignment of unique participant number
  - 4.2.1 Each patient will be identified with a unique participant number (UPN) for this study. All data will be recorded with this identification number on the appropriate case report form (CRF).
- 4.3 Randomization
  - 4.3.1 Patients will be randomly assigned to one of the three groups: SC, IVI or Control. The randomization will be performed in 1:1:1 ratio in blocks of 6, with no stratifications.

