### 8.2 Secondary outcome measures

- 8.2.1 Intraoperative supplementary analgesia
- 8.2.2 Intraoperative hypo/hypertension and brady-/tachycardia
- 8.2.3 Maximum intraoperative pain (NRS)
- 8.2.4 Adverse effects intraoperatively and at approximately 2 and 6 hours postpartum
- 8.2.5 Plasma concentrations of ketamine at baseline and approximately 20, 40 and 100 minutes postpartum. Samples will be centrifuged and the extracted plasma samples will be stored at -80 degrees Celsius before transfer to the metabolomics laboratory at Washington University for ketamine assay.
- 8.2.6 Total opiate consumption in the first 2 days postpartum
- 8.2.7 Surgical site pain (NRS 0-10), by face-to-face or telephone interview, at 2, 6, 24 and 48 hours after delivery and on postpartum days 21 and 42.
- 8.2.8 EPDS and GAD-7 on postpartum days 1 and 2, by face to face interview, and days 21 and 42, by telephone interview.
- 8.2.9 Apgar scores
- 8.2.10 Admission to NICU
- 8.2.11 Breastfeeding success (Y/N) on post-operative days 1 and 2

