## 9 STATISTICAL METHODS

### 9.1 Sample size and analysis

No formal sample size has been performed as this is a pilot designed to establish the feasibility of an RCT. Preliminary data from this study will be used to inform the sample size calculation for the subsequent clinical trial. Descriptive statistics will be employed to present the demographic data. Continuous variables will be summarized using means (SD) or medians (IQR), as appropriate. After construction of the concentration-time curves for each patient, the peak plasma concentration and area under the concentration-time curve will be summarized overall and associations with both antidepressant effect and incidence of adverse symptoms will be explored.

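### Blood pressure and pulse enter the outcomes only as counts beyond fixed limits; with 20 women per arm these say little, and summaries of the recorded values should be added beside them

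*Combined protocol and SAP*

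**What the plan says.** - Synopsis, Measurements: "Baseline and intraoperative vital signs" are listed as a measurement in their own right. No reading times, frequency or summary are given.
- Section 6, Measurements, item 6: the body of the protocol turns this into "Incidence of hypo- or hypertension (systolic BP < 80 or > 170 mmHg, respectively". The same item cuts the pulse readings in a similar way, at values under 40 and over 120 bpm.
- Section 8.2.2: the secondary outcome is "Intraoperative hypo/hypertension and brady-/tachycardia", that is, the same event categories.
- Section 7, Table 6: there is no row for vital signs.
- Section 9.1: "Continuous variables will be summarized using means (SD) or medians (IQR), as appropriate". The sentence names no vital sign, no per-patient summary and no contrast between arms.
- Size: the Synopsis plans "60 patients (20 in each of the subcutaneous [SC], intravenous [IVI] and control [P] groups". Section 9.1 adds that "No formal sample size has been performed as this is a pilot designed to establish the feasibility of an RCT". No expected rate is given for any of the four limits, and no SD for pressure or pulse.

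**The concern.** A yes/no variable cut at an extreme keeps only the tail of the distribution. Two women whose systolic pressure changes by very different amounts are recorded alike if both stay between 80 and 170 mmHg, and the baseline reading plays no part in the definition. With 20 women per arm, the report of 8.2.2 may be a table of very small counts that neither describes what each route does to pressure and pulse nor rules out appreciable event rates.

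What is at stake is descriptive. Section 1.3 says the pilot is meant to collect preliminary tolerability data on the two routes, and pressure and pulse are not among the adverse effects in Table 5. Section 8.2.2 is therefore the only outcome through which a haemodynamic difference between the subcutaneous, intravenous and placebo arms would be described. Counts also yield no SD for planning later work. For intraoperative pain the protocol already keeps a per-patient maximum (item 7 of the same list); pressure and pulse get no such summary.

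**Working it through.** The plan states no power, rate or precision for this outcome, so there is no figure to reproduce.

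**Inputs from the documents.** n = 20 per arm (Synopsis; Table 2), allocated 1:1:1 (section 4.3); limits of 80 and 170 mmHg and of 40 and 120 bpm (section 6, item 6).

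**Inputs assumed.** The rate p at which women cross a given limit, shown over a range. The SD of systolic pressure or of its change, 10 to 20 mmHg.

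**1. Chance that an arm shows no event at a given limit**, (1 − p)^20:

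| Assumed p | P(0 of 20) |
|---|---|
| 1% | 0.82 |
| 2% | 0.67 |
| 5% | 0.36 |
| 10% | 0.12 |
| 15% | 0.04 |
| 20% | 0.01 |

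An empty arm is more likely than not only if p is below 1 − 0.5^(1/20) = 3.4%.

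**2. What an empty arm rules out.** The exact two-sided 95% upper limit for 0/20 is 1 − 0.025^(1/20) = 16.8%. The one-sided limit is 1 − 0.05^(1/20) = 13.9%.

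**3. What separates two arms on counts.** The two-sided Fisher p for k/20 against 0/20 is 2 × C(20,k)/C(40,k).
- k = 4: 2 × 4,845/91,390 = 0.106.
- k = 5: 2 × 15,504/658,008 = 0.047.

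So at least 5/20 against 0/20 is needed. Exact Fisher power at 20 v 20 is 7% for 5% v 15%, 17% for 5% v 20%, 24% for 10% v 30% and 45% for 5% v 30%. No test is planned; power is used here only as a measure of information.

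**4. Precision with the values themselves.** The t-based 95% half-width for a difference between two arms is t(0.975; 38 df) × SD × sqrt(2/20) = 2.024 × 0.3162 × SD = 0.640 × SD.

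| Assumed SD (mmHg) | Half-width (mmHg) | Power for a 10 mmHg shift |
|---|---|---|
| 10 | 6.4 | 89% |
| 12 | 7.7 | 75% |
| 15 | 9.6 | 56% |
| 20 | 12.8 | 35% |

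**5. Both approaches on the same hypothetical data.** Suppose peak systolic pressure is normal with mean 130 and SD 15 mmHg on placebo, and 10 mmHg higher on ketamine (all assumed). The rate above 170 mmHg is 1 − Φ(40/15) = 0.4% on placebo and 1 − Φ(30/15) = 2.3% on ketamine. The ketamine arm then shows no event with probability 0.63. Fisher power on the counts is essentially 0%, against 56% for the comparison of means.

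Over placebo means of 120, 130 and 140 and SDs of 12, 15 and 20 mmHg, the chance of an empty ketamine arm runs from 0.03 to 0.99. Fisher power never exceeds 6%, while the comparison of means has 35% to 75%. The frequency of empty arms thus depends heavily on the assumptions; the advantage of the continuous comparison holds throughout this range.

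**The case against.** **A reader might infer that the table will usually be empty.** The documents give no rate, so they do not support this. Even at 5% an arm has at least one event at that limit with probability 1 − 0.36 = 0.64, and at 15% to 20% an empty arm is rare. The four limits together are less sparse than each alone: if each were crossed independently by 2% to 5% of women (assumption), an arm would have no event of any kind with probability 0.98^80 = 0.20 to 0.95^80 = 0.02. The statement has to be conditional and made per limit. Steps 2 and 3 do not need an assumed rate.

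**A reader might infer that the readings are discarded.** That also goes too far. The Synopsis lists vital signs separately, and the general sentence in 9.1 could be read to cover them. Section 10.1 counts any abnormal sign as an adverse event, and 10.3 asks for intensity and relationship to study drug, so a notable change inside the limits need not be lost. What stands is that no continuous haemodynamic outcome, per-patient summary or arm contrast is defined.

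**A reader might infer that a pilot objective or milestone is compromised.** Objective 2.3 concerns the design of an efficacy trial and does not ask for a haemodynamic comparison of routes. FM1 to FM4 do not name pressure or pulse.

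**The alternative is itself imprecise and needs more than a line of text.** Both points stand. A half-width of about 10 to 13 mmHg cannot exclude a moderate difference. Reading times are unspecified, baseline is not tied to the moment before study drug, and the largest change grows with the number of readings. Item 5 records only analgesic and sedative doses, so other treatment affecting pressure would not be known when the results are read.

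**Counting marked excursions is a legitimate safety outcome in a pilot.** Agreed. Nothing here argues for demoting the counts or changing the limits.

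**Conclusion.** The point holds as a minor improvement. The only haemodynamic outcome defined is a set of four threshold counts, and at 20 per arm such counts are weak: 0/20 leaves rates up to 16.8% open, and nothing short of 5/20 against 0/20 separates two arms at the 5% level. These two results need only the arm size. That an arm has no event at a given limit with probability 0.36 or more is conditional on a true rate of 5% or less for that limit, which is an assumption.

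Summaries of the recorded values would tell more, with a 95% half-width of about 9.6 to 12.8 mmHg for an assumed SD of 15 to 20 mmHg. That supports descriptive estimates, and it would not settle whether the routes differ. The outcome is secondary, and no feasibility decision turns on it.

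**What to change.** 1. **Section 8.2.2.** Keep the four threshold counts as they are. Add, for each woman, the largest rise and the largest fall in systolic pressure and in pulse during surgery, measured from the last reading before study drug.
2. **Section 9.1.** State that the counts will be reported by arm with exact (Clopper-Pearson) 95% intervals. State that the four change variables will be summarised by arm, with mean differences and t-based 95% intervals for SC v placebo, IVI v placebo and SC v IVI. That gives 4 × 3 = 12 intervals, to be labelled descriptive and not adjusted for multiplicity.
3. **Section 7, Table 6.** Add a vital-signs row that states a recording interval and observation window common to all three arms, and identifies the pre-dose reference reading. Without a common interval, an arm with more readings would tend to show larger extremes. A reference taken before the neuraxial block would mix any effects of the block and delivery into the change.

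The cost is a short addition to two sections, one table row and a small derivation. Whether extra readings are needed cannot be told from the documents, because the present reading times are not stated. The sample size and the four milestones do not change.

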## 8 OBSERVATIONS AND MEASUREMENTS

### 8.1 Primary outcome measures

- 8.1.1 **FM1:** Establish that the incidence of PPD in our cohort is >10%
- 8.1.2 **FM2:** Achieve the recruitment of >50% of approached patients to demonstrate feasibility for an RCT
- 8.1.3 **FM3:** Ensure that the design of assessments and data collection make it possible to achieve a complete dataset in >90% of participants
- 8.1.4 **FM4:** Ascertain that neither of the chosen routes of administration of ketamine are intolerable to patients, as defined as the incidence of one or more severe side effects experienced by >10% of participants in that study arm.

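### FM4 judges whether the subcutaneous route is tolerated, but no solicited, severity-graded item asks about the injection site, and the plan does not say whether unsolicited adverse events count

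*Combined protocol and SAP*

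**What the plan says.** The synopsis hypothesis includes the claim that "the subcutaneous route is well tolerated and has a favorable pharmacokinetic profile". FM4, a primary outcome in 8.1.4 that also appears in 5.1.4, is worded: "Ascertain that neither of the chosen routes of administration of ketamine are intolerable to patients". The same milestone then sets its criterion for calling a route intolerable: "as defined as the incidence of one or more severe side effects experienced by >10% of participants in that study arm". Section 5.1 makes attaining the milestones a condition for going on to the larger trial.

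All three arms receive a subcutaneous injection and an intravenous infusion; only the SC arm receives ketamine subcutaneously. On preparation, the synopsis states: "The s/c injectate will be administered undiluted". The intravenous injectate is diluted to 40 ml.

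Adverse effects are solicited in item 8 of the section 6 measurements: "Incidence of the signs/symptoms in Table 5 will be assessed intraoperatively and approximately 2 and 6 hours after delivery". The grading scale for these ratings is given in the next sentence of that item: "The presence of each adverse effect will be assessed using a 4-point scale (absent, mild, moderate, severe". Table 5 lists nausea, vomiting, pruritus, dizziness, sedation, shivering, anxiety, euphoria, hallucinations, amnesia, blurred vision, diplopia and nystagmus. It has no injection-site item and no row for other effects. The matching secondary outcome, 8.2.4, has the same time points: "Adverse effects intraoperatively and at approximately 2 and 6 hours postpartum".

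Separately, 10.1 defines an adverse event broadly. Section 10.3 requires every adverse event to be reported, with a description that covers intensity and relationship to study drug.

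**The concern.** FM4 turns on how many participants in an arm have a severe effect, so its result depends on which effects are asked about and graded. Table 5 carries the only scale in the documents with a severe category, which makes it the natural source for FM4, and it has nothing on the injection site. The other pain measures are maximum intraoperative pain and surgical-site pain; neither refers to the subcutaneous injection.

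The SC arm is the only one with undiluted ketamine under the skin, so a local effect of the drug is one way in which the two ketamine arms could differ. The plan does not set out to measure it. If local reactions are recorded only when volunteered or noticed, while 13 other effects are asked about and graded, the ascertainment is uneven and the error favours the subcutaneous route. Ratings that were not collected cannot be recovered afterwards, so the gap has to be closed before enrolment or early in it.

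**Working it through.** The plan gives no sample-size basis, error rate or power for FM4, so there is no stated figure to reproduce.

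**Inputs**
- Arm size: 20 (section 6.1, Table 2).
- FM4 limit: more than 10% of an arm with at least one severe effect (5.1.4, 8.1.4).
- True rate *p* of severe injection-site reaction: not in the documents; assumed, 2% to 30%.
- True rate of any severe Table 5 effect in the SC arm: not in the documents; 5% assumed for illustration, independent of local reactions.

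**Step 1. Cut-off.** 2/20 = 10% does not exceed 10%; 3/20 = 15% does. FM4 fails an arm at 3 or more of 20.

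**Step 2. Local reactions alone, fully solicited and counted.**

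P(X ≥ 3) = 1 − [(1−p)^20 + 20p(1−p)^19 + 190p²(1−p)^18]

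At p = 0.10: 1 − (0.1216 + 0.2702 + 0.2852) = 0.32.

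| Assumed true severe local rate | Chance that FM4 fails the arm |
|---|---|
| 2% | 0.01 |
| 5% | 0.08 |
| 10% | 0.32 |
| 15% | 0.60 |
| 20% | 0.79 |
| 30% | 0.96 |

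**Step 3. Partial capture.** Suppose the true rate is 20% but general reporting picks up and counts only half of the reactions (an assumption). The effective rate is 0.20 × 0.5 = 10%, and the chance of failing falls from 0.79 to 0.32.

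**Step 4. Together with Table 5 effects.** With a 5% severe Table 5 rate and a local rate q, the combined rate is 1 − 0.95(1 − q).

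| q | Combined rate | Chance of failing, local counted | Chance of failing, local not counted |
|---|---|---|---|
| 5% | 9.75% | 0.31 | 0.08 |
| 10% | 14.5% | 0.57 | 0.08 |
| 20% | 24% | 0.89 | 0.08 |

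Whether local reactions are sought and counted can therefore decide the milestone, unless they are rare.

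**The case against.** The strongest reply is that the plan does not exclude local reactions. FM4 does not cite Table 5, and nothing calls that table exhaustive. Under 10.3 the investigator is to monitor closely for adverse events and report all of them with intensity, and no 6-hour limit is set. The definition in 10.1 would cover a local reaction, so a severe one reported this way fits FM4's wording. This stands. A reader might infer that FM4 works from a closed list, that local harm cannot count, or that the route could pass with every participant severely affected. Those readings hold only if FM4 is confined to Table 5, and the documents do not say that it is. What remains is that 10.3 schedules no injection-site question, sets no grading scale and does not say whether its events enter FM4. Two analysts could reach different FM4 results from the same records.

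Other limits also stand:

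- The documents report no local reactions to subcutaneous ketamine and no rate for them.
- They do not give the injection site or the duration of the block, so it cannot be argued from them that a reaction would be masked until sensation returns.
- Pruritus is not restricted to generalised itch, so Table 5 should not be called wholly systemic.
- FM4 is an absolute limit per arm with no subtraction of the saline arms, so any added item raises the chance of failing.

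A reader might extend the point to item 6 ("Incidence of hypo- or hypertension (systolic BP < 80 or > 170 mmHg, respectively" and the pulse limits), which has no severity grade. That is a separate matter: those events have numeric thresholds and are their own secondary outcome (8.2.2), and no text bars them from FM4.

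**Conclusion.** The point holds as a gap in ascertainment and definition. Injection-site reactions are neither solicited nor graded on the scale that supplies the severe category, and FM4 does not say which adverse events it counts. The likely direction of error is towards passing the subcutaneous route.

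The size cannot be fixed from the documents. For local reactions alone, the chance of tripping FM4 if they were solicited and counted runs from 0.01 at an assumed 2% severe rate, through 0.32 at 10%, to 0.96 at 30%. If such reactions are rare, the gap matters little; at 10% or more it could change the decision. These figures assume 20 evaluable participants in the arm and independence between participants; Step 4 also assumes independence between local and Table 5 effects.

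The change should be made, because FM4 is a primary milestone and the missing ratings could not be reconstructed.

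**What to change.** 1. Add *injection-site reaction (pain, redness, swelling)* to Table 5 on the existing 4-point scale.
2. Rate it at 2 and 6 hours and at the existing 24- and 48-hour contacts, in all three arms. Update Table 6 and 8.2.4 to match.
3. State in 5.1.4 and 8.1.4 that a severe rating on this item counts in FM4, and whether severe adverse events reported under 10.3 also count.
4. Tabulate the item by arm. The IVI and P arms both receive a saline subcutaneous injection, so they give a blinded comparison for the SC arm without extra procedures.

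The cost is one CRF line at four contacts that already take place, and a clause in FM4. The downside is that FM4 becomes harder to pass, by an amount that depends on the unknown local rate. In the illustration above, a 5% local rate raises the chance of failing from 0.08 to 0.31 although the combined true rate, 9.75%, is below the limit. The tabulation against the saline-injected arms would help in reading such a result.
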